## 5.7 Withdrawal of Subjects

Participants may be withdrawn from the study without their consent if the PI feels that it is unsafe for the participant to continue to participate, or if they refuse the blood draw. Participants may withdraw from the study at any time by contacting study staff either in writing or by calling the study hotline.

## 6.0 Project Timeline

	Year 1 – 2016		Year 2 – 2017				Year 3 – 2018			
	(quarter)		(quarter)				(quarter)			
	3	4	1	2	3	4	1	2	3	4
Protocol development, IRB approval, personnel hiring/training	X	X								
Contracting with Progenity		X								
RCT recruitment and enrollment			X	X	X	X	X	X		
RCT data collection (9 month follow-up)							X	X	X	
RCT data analysis										X
Final report preparation										X

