## 3.0 Objectives

PGx testing could greatly improve the use of antidepressants by aiding prescribers in identifying proper medications for individual patients; thus potentially improving medication adherence, as well as reducing symptoms and antidepressant side effects.

This pilot study will explore the use of PGx testing in primary care, and is guided by several specific aims:

Specific Aim 1: To determine the effect of PGx testing on the primary outcome of physician treatment decisions, as measured by the change in the proportion of patients who are prescribed medications at baseline that are contraindicated according to the PGx test, compared to the proportion at six-month follow-up.

Specific Aim 2: To determine the effect of PGx testing on secondary outcomes measures of interest, including change in symptoms and severity and medication adherence from baseline to six-month follow-up.

Specific Aim 3: To determine the acceptability of PGx testing in primary care among patients and physicians.

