Patient participants will meet with study staff for consent and baseline data collection at a Michigan Clinical Research Unit (MCRU) in either Domino's Farms or the Cardiovascular Center. Once consent and baseline data collection are complete, participants will have their blood drawn by MCRU laboratory staff. A single 4 mL Lavender top EDTA tube of blood will be drawn. Once the blood draw is complete, study staff will send the sample to Progenity for analysis. After the baseline assessment is complete, patient participants will be randomized equally to either have their test results sent immediately to their participating primary care physicians once available, or to have their test results sent in three months. Randomization will be stratified by physician in ten block units to ensure balance by physician. PharmDs on the research team ([name] and [name]) will be available to consult with physician participants at any time during the study; however, our study PharmDs will meet with each participating physician at least once, when their first patient PGx test results are available to provide general, as well as patient specific education about the PGx test and results. These consultations will help physicians to interpret PGx test results, and may help to guide treatment decisions, if necessary. Study pharmacists or staff will not

provide PGx results to patients; it is up to the patient's physician to provide this information if he/she feels it is appropriate. Likewise, although study pharmacists may make treatment recommendations based on the PGx test results, it is up to the treating physician to decide whether to act on those recommendations. All intervention patient participants will be followed for a total of 6 months, with phone-based follow-up assessments occurring at 3- and 6-months. All control patients will be followed for 9 months, with phone-based follow-up assessments occurring at 3-, 6-, and 9-months. Please see Figure 2 for patient participant study flow.

Figure 1. Physician Participant Study Flow

[figure not shown]
[figure not shown]

Figure 2: Patient Participant Study Flow

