## 5.6 Data Analyses

In this study, we expect to enroll up to 30 physician participants and expect a retention rate of 90-100%. We also expect to enroll about 100 patient participants and expect a retention rate of 80% at the completion of this study.

Data from this study will be analyzed by the study statistician. Survey data will be analyzed using descriptive statistics. Multiple-choice questions will be analyzed using standard quantitative techniques including Chi square and t-test. Open-ended responses will be independently coded using qualitative methods, including any transcripts that result from the recorded survey responses.

Independent sample t-tests will be used to compare outcomes between intervention and control groups at each time point, as well as at similar time points after test results were released to physicians (i.e. baseline for intervention vs. 3 month for control group). Linear mixed models will assess the change in outcomes, as well as whether the change is similar between groups. This will be done by including time, study group, and a time by study group interaction as predictors of each outcome. Time will be considered in two ways, first as the time in study, and secondly as time since test results were released to physicians. In the latter, only data from 3-month to 9-month will be included for the control group, and baseline to 6-month for intervention group, due to timing of test result release. Models will be adjusted for patient demographics.

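### The project timeline ends data collection one quarter after enrolment closes, which contradicts the 6- and 9-month follow-up in section 5.1

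*Combined protocol and SAP*

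**What the plan says.** The timeline in section 6.0 marks three activities that matter here, in whole quarters:

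- "RCT recruitment and enrollment": Q1 2017 through Q2 2018.
- "RCT data collection (9 month follow-up": Q1 2018 through Q3 2018.
- "RCT data analysis", together with the final report: Q4 2018, the last column of the table.

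Section 5.1 sets the follow-up without exception for late enrollees: "All intervention patient participants will be followed for a total of 6 months", and "All control patients will be followed for 9 months, with phone-based follow-up assessments occurring at 3-, 6-, and 9-months".

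Three other statements depend on those calls. Aim 1 in section 3.0 takes the baseline proportion "compared to the proportion at six-month follow-up", and Aim 2 also runs from baseline to six months. Section 5.6 uses control data from month 3 to month 9 in the model that counts time from release of the test results. The same section says of about 100 patients that the investigators "expect a retention rate of 80% at the completion of this study".

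**The concern.** Only one quarter separates the end of enrolment from the end of data collection, while the longest follow-up is three quarters. If staff follow the calendar, the last enrollees lose scheduled calls for a reason that has nothing to do with dropout.

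The loss falls in two places. The first is month 6, the time point for Aims 1 and 2, in both arms. The second is month 9 in the control arm. Controls' results are released at month 3, so month 9 is their only assessment six months after release, the counterpart of month 6 in the intervention arm. A control enrolled in Q2 2018 would have only the baseline and month-3 calls, and so would contribute no call later than the release of results to the time-since-release model. The loss depends on enrolment date and, for the last call, differs between the arms.

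**Working it through.** **Inputs**

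- Enrolment: six quarters, months 0 to 18 counted from 1 January 2017 (section 6.0).
- End of data collection: end of Q3 2018, month 21 (section 6.0).
- Last scheduled call: month 6 for intervention, month 9 for control (section 5.1).
- Patients: about 100, randomized equally, taken as 50 per arm (sections 5.1 and 5.6).
- Expected retention: 80% (section 5.6). It is given as an expectation without inputs or a formula, so there is no calculation to reproduce.
- Accrual pattern: not stated. Uniform accrual is an assumption, and two other shapes give a range.
- Calls are taken at their nominal dates.

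**Step 1: last enrolment date that fits**

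- Month-3 call: 21 − 3 = month 18, the end of June 2018. Everyone can have it.
- Month-6 call: 21 − 6 = month 15, the end of March 2018. All Q2 2018 enrollees miss it.
- Month-9 call (controls): 21 − 9 = month 12, the end of December 2017. All controls enrolled in Q1 or Q2 2018 miss it.

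**Step 2: share who can reach each call, before any dropout**

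With t the last enrolment month that fits, the share enrolled by t is t/18 for uniform accrual, 1 − (1 − t/18)² for accrual falling linearly to zero, and (t/18)² for accrual rising linearly from zero. The last column is the mean of the intervention share at month 6 and the control share at month 9.

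| Accrual | Reach month 6 | Controls reaching month 9 | Reach own arm's last call |
|---|---|---|---|
| Uniform | 15/18 = 83.3% | 12/18 = 66.7% | 75.0% |
| Linearly declining | 1 − (3/18)² = 97.2% | 1 − (6/18)² = 88.9% | 93.1% |
| Linearly rising | (15/18)² = 69.4% | (12/18)² = 44.4% | 56.9% |

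In patients, under uniform accrual, about 17 of 100 (100 × 3/18) miss month 6 and about 17 of 50 controls (50 × 6/18) miss month 9.

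**Step 3: set against the 80%**

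- Uniform accrual with 20% dropout on top: 0.833 × 0.8 = 67% at month 6, 0.667 × 0.8 = 53% of controls at month 9, and 0.75 × 0.8 = 60% at the last call.
- Uniform accrual: 80% at month 6 would need dropout of no more than 1 − 0.8/0.833 = 4%. At the last call the ceiling is already below 80%.
- Linearly declining accrual: 80% at the last call is possible with dropout up to 1 − 0.8/0.931 = 14%.

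**Step 4: more lenient readings of the row**

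- Suppose calls continue through the analysis quarter, to month 24. Everyone then reaches month 6. Controls enrolled in Q2 2018 still reach month 9 only in Q1 2019, outside the table. Under uniform accrual, 15/18 = 83.3% of controls reach month 9 and (100 + 83.3)/2 = 91.7% of patients reach their last call.
- Suppose the row covers only the 9-month calls. These would run from Q4 2017 (for Q1 2017 enrollees) to Q1 2019 (for Q2 2018 enrollees). The row runs from Q1 to Q3 2018, so neither end fits.

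**The case against.** The strongest reply is that the row is a coarse planning bar and not a cut-off. It starts in Q1 2018, a year after enrolment opens, so read literally it also excludes every assessment due in 2017, which sections 5.1 and 5.5.2 require. It may simply not have been updated. Nothing in the protocol says that calls stop at the end of September 2018, and section 5.1 says that all patients are followed. This stands as a reason to treat the point as a contradiction to be reconciled, not as proof that data will be lost. It does not remove the contradiction, because no reading in Step 4 makes the table and section 5.1 agree.

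A reader might also infer three stronger things that the documents do not support.

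- **That 80% retention is impossible.** This depends on accrual, which is not stated. With declining accrual the ceiling is about 93%. Section 5.6 also does not say whether a patient whose last call falls after collection closes counts as not retained.
- **That a promised six months of safety follow-up after release is broken.** No section makes that promise. It could only be inferred from the month 3 to 9 analysis window and from the side-effect checklist scheduled at each assessment in Table 2.
- **That Aim 1 is lost for late enrollees.** Section 5.5.2 extracts medication changes from the chart independently of the calls, along with any routine PHQ-9 and GAD-7 scores. If extraction went on into Q4 2018 it could supply month-6 prescribing. It would not replace the phone-collected PHQ-8, SF-12, work productivity, side-effect and adherence measures, so Aim 2 is more exposed.

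Finally, this is a pilot with no power calculation, so the consequence is missing and uneven data rather than a missed power target.

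**Conclusion.** The contradiction between sections 6.0 and 5.1 is real and rests on calendar dates alone. On the table as written, Q2 2018 enrollees in both arms have no month-6 call, and controls enrolled in either quarter of 2018 have no month-9 call. Its size depends on accrual. The uniform-accrual ceiling on reaching the last call is 5 percentage points below the expected 80% before anyone drops out, and the plausible range lies on both sides of 80%. The expectation in section 5.6 is therefore unsupported by the calendar, but not refuted by it. The figures also assume equal arms of 50, calls at nominal dates and a literal end to collection in Q3 2018.

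**What to change.** Reconcile section 6.0 with section 5.1. Run the data-collection row from the first enrolment in Q1 2017 to the end of Q1 2019, which is nine months after the last Q2 2018 enrolment, and move analysis and the final report to Q2 2019. Moving only the end of the row would leave the 2017 assessments outside it. Extending by one quarter would still miss the last controls.

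If the end date cannot move, restate expected completion in sections 5.1 and 5.6 by arm and visit as the calendar allows, and say whether retention counts calls not made because collection had closed. Closing enrolment at the end of 2017 does not look like an available alternative: the reference list cites a web page accessed in 2018, so the text was still being edited after that date.

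The cost is a calendar amendment and a report about two quarters later. The calls are already planned, so no new patients, visits or procedures are needed.

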## **7.0 Reporting**

Participants will be requested to call the study hotline to report any adverse events (AEs) or unanticipated problems. All staff will be directed to report any serious (SAEs), protocol deviations, and unanticipated problems to the Project Coordinator as soon as possible. The Project Coordinator or the PI will submit the appropriate documentation to the UM IRB or other department as required.

## **8.0 Privacy and Confidentiality**

This study will utilize PHI including the following elements: name, date of birth, full mailing address, clinic dates, phone numbers, email addresses, social security numbers, medical record numbers. All study staff-generated electronic study data including participant identifiers will be securely maintained in REDCap, or a UM restricted server, in an access-limited folder, with access given only to specified project staff. All participants will be assigned a study ID, which will be associated with their survey data. Although we will maintain a file that links patient MRN and study ID, this will be kept separate from other study data, in a manner consistent with UM policies for PHI. The results of the Progenity Informed PGx tests will be transmitted back to study staff via secure means such as MiShare and stored securely in access-limited folders. All paper records and audio recordings and equipment with patient identifiers will be kept in a locked office, in locked file cabinets. Access to the file cabinets will be restricted to approved study personnel.

PHI sent to Progenity as part of ordering the PGx test is protected as required by the contract.

## **9.0 Communication Plan**

Prior to the start of this study, the research team will complete the process for obtaining approval to recruit participants from UM DFM clinical sites, which includes obtaining permission from the UM DFM Associate Chair for Research ([name]), as well as clinical site medical directors.

Any proposed changes to the study protocol which would change the role of the recruitment sites will be communicated via email to UM DFM Associate Chair for Research and the clinical site medical directors and agreed upon prior to seeking IRB approval.

UM DFM Associate Chair for Research and the relevant clinical site medical director will be informed via email once recruitment at each individual site has been closed.

